7.1.4 Deaths

Any deaths that occur from the time of informed consent to the follow-up visit, regardless of attribution, must be reported within 24 hours of investigator's awareness of the death. See Safety Form Completion Instructions for complete instructions.

The Sponsor should be provided a copy of any post-mortem findings and/or relevant medical reports, including histopathology.

7.1.5 Pregnancies and Contraception Requirements for Females

For the purposes of this study, a female of childbearing potential is defined as any female who has experienced menarche and is pre-menopausal, unless permanently surgically sterile (e.g., hysterectomy, bilateral salpingectomy, bilateral oophorectomy). A postmenopausal state is defined as no menses for 12 months without an alternative medical cause in a previously menstruating female.

For the purposes of this study, acceptable contraception is defined below based on *Nonclinical Safety Studies for the Conduct of Human Clinical Trials and Marketing Authorization for Pharmaceuticals: ICH M3(R2)* dated January 2010, and other available guidelines ([“U.S. Medical Eligibility Criteria for Contraceptive Use” 2010](#); [“Recommendations related to contraception and pregnancy testing in clinical trials” 2014](#); [“M3\(R2\) Nonclinical Safety Studies for the Conduct of Human Clinical Trials and Marketing Authorization for Pharmaceuticals” 2010](#)):

All female subjects of childbearing potential must use highly effective contraception, which includes the use of one or more of the following acceptable methods:

1. Surgical sterilization (e.g., bilateral tubal occlusion or ligation, hysterectomy, bilateral salpingectomy, bilateral oophorectomy)
2. Total (as opposed to periodic or cyclic) abstinence from heterosexual intercourse, only if planned for the entire duration of the study period and consistent with the preferred and usual lifestyle for the subject
3. Hormonal contraception associated with consistent inhibition of ovulation; these may include (but are not necessarily limited to) oral, intravaginal, implantable, injectable, or transdermal delivery methods
4. Intrauterine device/system
5. Exclusive (sole) monogamous intercourse with a sterilized (i.e., vasectomized) or otherwise non-fertile (e.g., castrated) male partner; the male partner must have received medical assessment of the surgical success

Progesterone-only oral contraceptives are excluded as a highly effective method of contraception, as they do not consistently inhibit ovulation. Male or female condoms with or without spermicide, and female caps, diaphragms, and sponges with spermicide, or combinations (double barrier) are also excluded as highly effective contraceptive methods.

Any pregnancy occurring in a female subject or the female partner of a male subject, from the first study drug administration through the required follow-up visit must be reported within 24 hours of the investigator's awareness of the pregnancy. See Safety Form Completion Instructions for complete instructions.

The investigator will follow the pregnancy to delivery or other pregnancy outcome.

Pregnancy in a female clinical trial subject or female partner of a male clinical trial subject is not an SAE per se. Complications of such pregnancies (for example, spontaneous abortion) may qualify as SAEs and should be reported as such even if they occur after the Follow-up visit. Any congenital anomalies/birth defects must be recorded and reported as SAEs. See Safety Form Completion Instructions for complete instructions.

7.1.6 *Worsening of Pruritus or PN*

Pruritus or PN should be recorded as an AE or SAE only if considered by the investigator to have worsened in severity beyond the subject's typical fluctuations. It is important to include a description of the nature of the unexpected worsening when recording the AE or SAE (e.g. new PN lesions in previously uninvolved skin).

7.2 **Methods and Timing for Recording and Reporting Adverse Events**

7.2.1 *Adverse Event Reporting Period*

Any AE occurrence during the study must be recorded on source documentation and eCRF at the site, in accordance with protocol instructions.

AEs and SAEs will be recorded from the first study drug administration through the follow-up visit. After the required follow-up visit, only SAEs that are believed to be drug-related should be reported.

After informed consent, but prior to initiation of study drug, only SAEs considered by the investigator to be caused by a protocol-mandated intervention will be collected (e.g. SAEs related to invasive procedures such as blood collection). These procedure-related SAEs should only be reported on the source documents and SAE form, not on the AE eCRF. Subjects who undergo screening procedures but are not randomized into the study will not have SAEs recorded in the clinical database.

7.2.2 *Eliciting Adverse Events*

Investigators will seek information on AEs and SAEs at each subject contact through the follow-up visit. All AEs and SAEs, whether reported by the subject or noted by authorized study personnel, will be recorded in the subject's medical record and on the AE eCRF page,

and, if serious, on the SAE form. For each AE and SAE recorded, the investigator will make an assessment of seriousness, severity, and causality.

7.2.3 Assessment of Severity

All AEs entered into the eCRF will be graded for severity using the National Cancer Institute Common Terminology Criteria for Adverse Events (NCI CTCAE) v4.03 (“[Common Terminology Criteria for Adverse Events \(CTCAE\)](#)” 2010) to describe the maximum intensity of the adverse event.

If the AE cannot be found in the event-specific NCI CTCAE grading criteria, the investigator should use the definitions for Grade 1, 2, 3, and 4 in [Table 1](#).

Table 1 Adverse Event Grading

Grade	Severity	Alternate Description ^a
1	Mild (apply event-specific NCI CTCAE grading criteria)	Asymptomatic or mild symptoms; clinical or diagnostic observations only; intervention not indicated.
2	Moderate (apply event-specific NCI CTCAE grading criteria)	Minimal, local or noninvasive intervention indicated; limiting age-appropriate instrumental activities of daily living (ADL ^b)
3	Severe (apply event-specific NCI CTCAE grading criteria)	Severe or medically significant but not immediately life-threatening; hospitalization or prolongation of hospitalization indicated; disabling; limiting self care ADL ^c
4	Very severe, life threatening, or disabling (apply event-specific NCI CTCAE grading criteria)	Life-threatening consequences; urgent intervention indicated.
5	Death related to AE	

^a Use these alternative definitions for Grade 1, 2, 3, and 4 events when the observed or reported AE is not in the NCI CTCAE listing. A semi-colon indicates ‘or’ within the alternate description of the grade.

^b Instrumental ADL refer to preparing meals, shopping for groceries or clothes, using the telephone, managing money, etc.

^c Self care ADL refer to bathing, dressing and undressing, feeding self, using the toilet, taking medications, and not bedridden.

Source: National Cancer Institute Common Terminology Criteria for Adverse Events (NCI CTCAE) v4.03

Note that severity, a measure of intensity, is not equivalent to seriousness, a regulatory definition of outcome. Regardless of severity, some AEs may meet the criteria for seriousness. See [Section 7.1.2](#) for the definition of an SAE.

If an adverse event changes in severity during the same study period (e.g., treatment period), only the highest severity grade will be recorded on the eCRF.

7.2.4 *Assessment of Causality*

The investigator's assessment of causality must be provided for all AEs (serious and non-serious). An investigator's causality assessment is the determination of whether there exists a reasonable possibility that the investigational product caused or contributed to an AE. Causality of an AE will be assessed by the investigator using the following terms:

- Likely Related: A reaction that follows a reasonable temporal sequence from administration of the study drug; that follows a known or expected response pattern to the suspected study drug; and for which other potential etiologies are considered less likely factors than the study drug.
- Likely Unrelated: A reaction that, considering all potential etiologies, is most likely due to factors other than the study drug.

7.3 Follow-up of Adverse Events and Serious Adverse Events

The investigator must make every effort to follow all AEs and SAEs regardless of attribution until judged resolved or stabilized, the subject is lost to follow-up, or it has been determined that study drug treatment or participation in the study is not the cause of the AE or SAE.

7.4 Reporting Serious Adverse Events to the Sponsor and Institutional Review Board or Ethics Committee

The Sponsor or designee is under obligation to report certain SAEs to regulatory authorities related to investigational drugs in clinical trials. The Sponsor or designee must be notified within 24 hours of an AE when the investigator determines that an AE meets the protocol definition of an SAE, regardless of the cause or relationship to study drug.

An SAE related to study participation occurring before study drug administration and after informed consent should be promptly reported to the Sponsor. If the investigator learns of any SAE at any time after a participant has been discharged from the study, and the SAE is considered likely related to study drug, the SAE should be promptly reported to the Sponsor.

Please see the Safety Form Report Completion Instructions for safety reporting instructions.

The investigator must also comply with applicable requirements concerning reporting of SAEs to the IRB or Ethics Committee (EC). This may include initial or follow-up notification of an SAE or other safety information.

7.5 Reporting Serious Adverse Events to Regulatory Authorities and Study Investigators

The Sponsor, or its designee, is responsible for submitting reports of serious, unexpected related adverse events to regulatory authorities on an expedited basis, according to the ICH E2A Guideline and to other regulatory authorities according to national and local regulations as required. The Sponsor, or its designee, is responsible for prompt submission to the IRB or EC of any expedited SAE reports submitted to regulatory authorities. All investigators

participating in ongoing clinical studies with serlopitant will receive copies of the SAE reports submitted on an expedited basis to regulatory authorities.

7.6 Emergency Unblinding

Emergency unblinding is available 24 hours per day/7 days per week and will be performed via IVRS. An investigator may unblind a subject's treatment assignment only when knowledge of the investigational product is essential for the welfare of a subject. There is no specific antidote for serlopitant and usual supportive medical management is recommended in the case of a medical emergency.

8 STATISTICAL METHODS

All statistical processing will be performed using SAS® unless otherwise stated. One interim analysis may be performed. Endpoints will be summarized with descriptive statistics by treatment group and visit. For continuous variables, the following information will be presented: n (number of subjects), mean, standard deviation, median, minimum and maximum. For categorical variables counts and percentages will be used. Summary statistics for imputed efficacy data will be reported based upon imputed data.

The primary method of handling missing efficacy data will be the method of Markov Chain Monte Carlo (MCMC) multiple imputation. Subjects who withdrew from the study due to a lack of efficacy, or used an excluded therapy to treat worsening of pruritus or PN, will be defined as non-responder.

As one sensitivity analysis, the last observation carried forward method (LOCF) will be used (i.e., the last available on-therapy observation for a subject will be used to estimate subsequent missing data points). As a second sensitivity analysis, a repeated measures model will be used on observed data. Additionally, a tipping point analysis will be done as a sensitivity analysis for the primary endpoint.

Baseline for measures other than the eDiary daily measures will be the last recorded value prior to the start of treatment. For daily measures including the WI-NRS, baseline will be the average result measured over the week prior to treatment.

A statistical analysis plan (SAP), describing all statistical analyses will be provided as a separate document. The SAP will be finalized prior to unblinding of the study treatments.

8.1 Decision Rule and Sample Size

This study will use a 5% two-sided alpha level. While the alpha level is two-sided, clinically relevant results require a serlopitant benefit. Statistical significance for the key secondary efficacy endpoints requires statistical significance for the primary efficacy endpoint (i.e. stepdown testing from primary to key secondary endpoints). The key secondary efficacy endpoints will be tested in order starting with the Week 4 WI-NRS 4-point responder rate, and then the Week 2 WI-NRS 4-point responder rate.

The target sample size of 280 randomized and dosed subjects (140 per group) has been determined based upon a 1:1 allocation of subjects to treatment groups and a 5% alpha level. Completed Phase 2 studies indicate that placebo responder rates vary between 20% and 25% and serlopitant rates between 33% and 47%. A sample size of 280 subjects provides >90% power assuming a placebo responder rate of **CCI** and a serlopitant rate of **CCI**.

The sample size calculations have been performed in PASS 13 (“[PASS 13 Power Analysis and Sample Size Software](#)” 2014) and use a Chi-Squared test. The primary analysis will control for the stratification factors. It is expected that this unstratified power estimate will under-estimate the true power as it does not take the variance reduction resulting from stratification into account ([Matts 1988](#)).

8.2 Handling of Missing Data

Should a determination of treatment period (on treatment, pre-treatment, follow-up) be required for adverse events or concomitant medication but the corresponding date is missing, or is a partial date, the event/medication will be considered on treatment unless the portions of the date that are available indicate this is not possible.

The primary method of handling missing efficacy data will be MCMC multiple imputation. Subjects who withdrew from the study due to a lack of efficacy, or used an excluded therapy to treat worsening of pruritus or PN, will be defined as non-responder. Imputation will be conducted within each treatment group independently, so the pattern of missing observations in one treatment group cannot influence missing value estimations in another. For each imputation process, 25 imputations will be performed.

If a subject fails to complete their eDiary for the week prior to Week 10, the primary endpoint (WI-NRS) data will be missing, unless the subject withdrew from the study due to a lack of efficacy, or the subject used an excluded therapy to treat worsening of pruritus or PN, in which case their responder status will be defined as non-responder. If the Week 10 value is missing for any other reason, the change from baseline value will be based on imputed data. Missing Week 10 WI-NRS values from which the 4-point responder status is derived will be estimated by MCMC.

Missing WI-NRS data will be derived for the analysis using the method of MCMC multiple imputation. Since both primary and key secondary efficacy endpoints require WI-NRS, the following steps will be followed:

1. Using the daily eDiary data, calculate Baseline and Week 2 through Week 10 values by averaging available values. In order to compute a week's average, a minimum of 4 values must be available for that week. The weekly average will be imputed when there are fewer than 4 values available.
2. From step 1, create a dataset for each treatment group, of subjects with observed values and those needing estimation by MCMC. The missing WI-NRS values in each dataset will be filled in using the MCMC method to generate 25 datasets. The resulting datasets for each treatment arm will be combined into one complete dataset.

Syntax:

```
proc mi data=datain out=dataout seed=&seed. Nimpute=25 <options>;  
  where trtpn=(TRT); /* Note TRT = [1, 2]; depending on treatment group */;  
  mcmc chain=single;  
  var baseline week1 week2 week3 week4 week5 week6 week7 week8 week9  
  week10;  
run;
```

3. From each complete dataset, the dichotomous responder rate will be determined. Each complete dataset will be analyzed as specified for the particular analysis.

Each complete dataset formed by multiply imputed data will be analyzed as specified for the particular analysis. The results from the analyses will be combined into a single inference using SAS® PROC MIANALYZE. In the case of the primary analysis and the secondary responder analyses, the Cochran Mantel Haenszel (CMH) statistics computed in the analyses of WI-NRS responder rates will be normalized using the Wilson-Hilferty transformation prior to combining them using SAS® PROC MIANALYZE

A total of 2 random seeds will be needed to impute missing data. Those random seeds have been pre-specified by using a random number generator:

- WI-NRS Serlopitant: Seed= 1537248074
- WI-NRS Placebo: Seed= 474752918

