#### Syntax:

```
proc mi data=datain out=dataout seed=&seed. Nimpute=25 <options>; where trtpn=(TRT); /* Note TRT = [1, 2]; depending on treatment group */; mcmc chain=single; var baseline week1 week2 week3 week4 week5 week6 week7 week8 week9 week10; run;
```

3. From each complete dataset, the dichotomous responder rate will be determined. Each complete dataset will be analyzed as specified for the particular analysis.

The results from the analyses will be combined into a single inference using SAS® PROC MIANALYZE. In the case of the primary analysis and the secondary responder analyses, the Cochran Mantel Haenszel (CMH) statistics computed in the analyses of WI-NRS responder rates will be normalized using the Wilson-Hilferty transformation prior to combining them using SAS® PROC MIANALYZE.

A total of 2 random seeds will be needed to impute missing data. Those random seeds have been pre-specified by using a random number generator:

• WI-NRS Serlopitant: Seed= 1537248074

• WI-NRS Placebo: Seed= 474752918

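### With 25 imputations per arm, a primary p-value close to 0.05 can fall on either side of the threshold depending on the imputation draw; about 1,000 would make this much rarer for little cost

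*Protocol*

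**What the plan says.** Protocol 8.2 and SAP 6.1.5 describe the same procedure. Weekly WI-NRS means based on fewer than four diary entries are imputed separately in each arm by MCMC. The number is given in the text ("For each imputation process, 25 imputations will be performed") and again in the code ("seed=&seed. Nimpute=25 <options>" in the SAP; the protocol has the same call). Responder status is derived in each completed dataset and a stratified CMH statistic is computed. These statistics "will be normalized using the Wilson-Hilferty transformation prior to combining them using SAS® PROC MIANALYZE". The result is judged under Protocol 8.1: "This study will use a 5% two-sided alpha level".

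Two seeds are printed, identical in both documents: "WI-NRS Serlopitant: Seed= 1537248074" and "WI-NRS Placebo: Seed= 474752918". Protocol 8.2 says of them: "Those random seeds have been pre-specified by using a random number generator". Neither document gives a reason for choosing 25, an expected share of missing Week 10 values, or a Monte Carlo error for the pooled p-value.

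**The concern.** A pooled statistic from 25 imputations has two sources of variation: the data, and the random draws used to fill the gaps. The second depends only on the seed and shrinks as more imputations are made. Near 0.05 it can decide whether the primary test is called significant. By the fixed testing order in Protocol 8.1 and SAP 6.1.8, it then also decides whether Week 4 and Week 2 may be tested. Fixing the seeds in advance stops anyone from choosing a favourable draw, but the draw still has an influence. A sponsor or regulator who reran a borderline analysis with other seeds might reach the opposite verdict from the same data.

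**Working it through.** **The plan's own figure.** The documents state no Monte Carlo error, so there is none to reproduce. The stated power above 90% cannot be reproduced exactly because the design rates are redacted. It is attainable within the Phase 2 range that the plan quotes: with 140 per group and a two-sided 5% chi-square test, 20% vs 40% gives 95.9%, while 20% vs 33% gives 69.5%.

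**Inputs.**
- From the documents: M = 25 imputations, 140 per arm, alpha 0.05, Wilson-Hilferty transformation and Rubin pooling.
- Assumed: 5, 10 or 20% of Week 10 values imputed per arm. In simulation these shares matched a between-imputation variance B of about 0.05, 0.10 and 0.21 on the Wilson-Hilferty scale, where the within-imputation variance is 1.

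**Step 1: SD of the p-value at p = 0.05.** The pooled statistic is t = mean(z) / sqrt(T), with T = 1 + (1 + 1/M)B. A chi-square p of 0.05 corresponds to an upper-tail z of 1.645. The delta method, allowing for the noise in both mean(z) and B, gives

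Var(t) = (B/M)/T + (1.645²/4) × [2B²/(M − 1)]/T²

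SD(p) = φ(1.645) × SD(t), with φ(1.645) = 0.1031.

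For B = 0.10 and M = 25:
- T = 1 + 1.04 × 0.10 = 1.104
- Var(t) = 0.00362 + 0.00046 = 0.00409, so SD(t) = 0.0639
- SD(p) = 0.1031 × 0.0639 = 0.0066

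| Assumed missing | B | SD(p), M = 25 | SD(p), M = 500 | SD(p), M = 1,000 |
|---|---|---|---|---|
| 5% | 0.05 | 0.0046 | 0.0010 | 0.0007 |
| 10% | 0.10 | 0.0066 | 0.0015 | 0.0010 |
| 20% | 0.21 | 0.0095 | 0.0021 | 0.0015 |

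Two simulations with different data models agree. Each imputed by arm from a normal model and then applied the stratified CMH test, the transformation and Rubin pooling. At 5, 10 and 20% missing, one gave SDs of 0.005, 0.007 and 0.011 with M = 25, and the other about 0.004, 0.007 and 0.010.

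**Step 2: how often a run crosses 0.05 when the many-imputation p is in 0.04–0.06.** Take p as uniform over the window and write a = 0.01/SD(p). The average crossing share is [aΦ(−a) + φ(0) − φ(a)]/a. At 10% missing, a = 0.01/0.0066 = 1.52 and the share is 24%. At 5% and 20% missing it is 18% and 31%. The larger simulation (80 borderline datasets per missing rate) gave 19, 25 and 32% at 5, 10 and 20%. The smaller one gave 22% at 10% and 37% at 20%, from only 12 and 18 borderline trials.

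With M = 1,000 the same formula gives about 3, 4 and 6%. The smaller simulation gave 2% at 10% missing and 17% at 20%. The latter rests on 18 trials, so a few lying very close to 0.05 can dominate it. It also shows that the dependence on the draw is not abolished.

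**Step 3: how often this matters overall.** By normal approximation, p lands in 0.04–0.06 in 1.6% of trials at 20% vs 40% and in 6.1% at 20% vs 33%. Direct counts of disagreement between 25 and many imputations (240 trials per setting) were:
- at assumed rates of 22% vs 42%: 0.9% with 10% missing, 1.2% with 20%, and 2.0% with a more extreme 30%;
- under the null: 0.8 to 1.0%;
- where the effect was tuned to a rejection rate of about 45 to 50%: 1.2% with 10% missing and 3.5% with 20%. The overall share can therefore exceed 2% if the true effect is well below the one planned for.

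**Step 4: type I error.** Null rejection rates with 25 versus many imputations were 4.1% vs 4.2%, 6.3% vs 6.7% and 4.9% vs 5.8% at 10, 20 and 30% missing. There is no sign of inflation.

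**The case against.** The strongest reply is that nothing here is invalid. The seeds are fixed identically in both documents, Rubin's variance already contains the 1/M term, and error rates are essentially the same with 25 as with many imputations. All of that stands. A reader might infer from the seed dependence that the test is biased, or open to choosing a seed after the fact. The pre-specified seeds and the null results do not support that reading.

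A second reply is that the crossing shares are conditional on an already borderline p-value, and that such results are rare. This also stands, which is why the overall share of about 1 to 2% belongs beside them.

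Third, the missing rate is assumed. Subjects who withdraw for lack of efficacy or use an excluded treatment for worsening are set to non-responder and add no Monte Carlo error. Only the remaining gaps count. Those need not be few, however. At the 70% diary completion required for entry, and assuming independent days, fewer than four of seven entries would occur in 12.6% of weeks; at 80% completion it would be 3.3%.

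Fourth, LOCF, the repeated-measures model and the tipping-point figure would show that a result is fragile. They help interpretation, but the primary p-value still decides.

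Two further inferences go too far. More imputations would not remove the noise, since it falls only as 1/sqrt(M). Nor does any significance call on the 3-point responder rates depend on it, because Protocol 8.8.3 and SAP 6.7.3 make those p-values descriptive.

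**Conclusion.** The point holds as a low-severity matter of precision. With 25 imputations the Week 10 p-value has a Monte Carlo SD of roughly 0.004 to 0.011 near 0.05, if 5 to 20% of Week 10 values are imputed. A many-imputation p between about 0.04 and 0.06 could then be called either way, with roughly 20 to 35% of runs crossing. The rate and the correlation of weekly scores are assumptions; the mechanism is not. The Week 4 and Week 2 key secondary tests use the same imputations and are exposed in the same way, but neither was simulated. It would be wrong to conclude that the seed decides this trial: that could happen only if the result came out close to the threshold.

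**What to change.** Before unblinding, replace 25 with about 1,000 imputations per arm in SAP 6.1.5 and Protocol 8.2: in the sentence giving the number, in the step that refers to 25 datasets, and in the code (Nimpute=1000). Keep both seeds and leave the rest of the analysis unchanged. At 10 to 20% missing this brings the SD of p to about 0.001 to 0.0015; 500 would give about 0.0015 to 0.002.

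Computing time for 280 subjects is trivial. The real cost is administrative. Under Protocol 9.1 and 9.6 an amendment needs investigator signatures and IRB or EC submission, at approximately 50 sites. If that is not worthwhile for this change alone, revise the SAP only and record the departure from the protocol in SAP section 8, which at present lists no changes. The same edit could fill in the options placeholder in the PROC MI call and state the input sort order, since the seeds alone may not fully fix the result.
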